## 1.2. Trial design

The trial has a prospective, multi-center, randomized, double-blind, controlled and cross-over design.

The Investigational Medicinal Products (IMPs) used during the trial are gadopiclenol and gadobutrol. Patients will perform a screening visit (V1) to confirm trial eligibility, then will be randomized in the trial to determine the order of IMP injection. The randomization scheme will allocate patients in a 1:1 ratio to the two series, gadopiclenol-gadobutrol or gadobutrol-gadopiclenol. Each of the 2 MRI visits (V2 and V4) will be followed by a safety visit (V3 and V5) performed 1 day after the MRI visit.

Images will be evaluated by prospective evaluation of the blinded images in a centralized and blinded manner. The blinded image evaluations (off-site read) will be performed by 3 independent blinded radiologists for the reading of random images and by 3 additional independent blinded radiologists for the global pairs assessment.

As different body regions are included in the study, readers with different expertise were needed for the reading of study images. Hence, according to the different anatomic locations, a pool of 18 readers are selected and qualified for the entire study images reads:

- 6 readers for Head and Neck (H&N): 3 readers for global pairs assessments, 3 readers for all other assessments
- 6 readers Thorax (including breast), Abdomen (including liver, pancreas and kidney), Pelvis (including uterus, ovary and prostate) put together and labelled as Body
- 6 readers Musculoskeletal (including extremities) (MSK)

Within each of the 3 groups, 3 readers are allocated for global pairs assessments, 3 other readers for all other assessments (such as lesion visualisation parameters). Each group of readers will only read images as labelled by specific anatomic locations (H&N, Body and MSK).

As statistical analysis will be performed on the whole set of patients, 1 reader from each expertise domain are put together (1 reader H&N + 1 reader Body + 1 reader MSK), 3 times. So, each reader presented in the report is a combination of 3 readers.

For almost all analyses including the 2 primary analyses, readers are put together based on the numbering (reader 1, reader 2 and reader 3) allocated by the imaging CRO in charge of the reading at the beginning of the trial before the start of the reading.

	Body	MSK	H&N
Reader 1= B1+MSK1+ H&N1	reader B1	reader MSK1	reader H&N1
Reader 2= B2+MSK2+ H&N2	reader B2	reader MSK2	reader H&N2

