### 3. STATISTICAL METHODS

#### 3.1. General considerations

With regards to the ICH topic E9 addendum, it has been decided to not use the wording estimand. Indeed, the protocol was drafted in 2018 when the addendum was not yet adopted by competent authorities (CA). Nevertheless, for this diagnostic cross-over study, all analyses and presentation asked by CA in this addendum were considered and put in place if needed. Hence, no strategy for dealing with intercurrent event is considered. However, sensitivity analyses are planned in order to assess the robustness of the primary analysis. As it is expected that very few patients dropped-out because of results of diagnostic of first period but rather for safety or technical reasons, no specific missing data handling is planned. However, a sensitivity analysis accounting for discontinued patient is planned (in the mixed models).

After the database lock, the statistical analysis will be performed by a Contract Research Organization ██████████ under the supervision of Guerbet biostatistician, on the basis of the present document.

A quality control of the statistical analysis will be performed by the CRO to ensure the reliability of the results prior to providing the results to Guerbet.

Some analyses will be presented by series (gadopiclenol-gadobutrol / gadobutrol- gadopiclenol), especially those about demographic and baseline characteristics. Some analyses will be presented by MR modality (pre /paired) and some by contrast agent group (gadopiclenol / gadobutrol), especially those in efficacy and safety. For the presentation by contrast agent group, efficacy analyses will be presented as randomized, that is to say presented by allocated contrast media whereas safety analyses will be presented by actually administered contrast media.

Tabulations of quantitative parameters will include the following summary statistics: Number of Patients / Mean / Standard Deviation / Minimum / Median / Maximum. If for a given parameter, the raw value has been collected with x decimal places, the mean, median and standard deviation will be rounded to x+1 decimal places, while the minimum and maximum values will be tabulated as reported with x decimal places.

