IMP deviation	Patient does not receive the IMP allocated by randomization	Clinical data base and IWRS data base	Major
	Patient does not receive the kit allocated by IWRS	Clinical data base and IWRS data base	Non major
	Patient having performed MRI examination but not administered with gadopiclenol	Clinical data base	Major
	Patient having performed MRI examination but not administered with gadobutrol	Clinical data base	Major criteria2
	The gadopiclenol volume actually administered is different from the theoretical one from 10 to 20%	Clinical data base and IWRS data base	Non major
	The gadobutrol volume actually administered is different from the theoretical one from 10 to 20%	Clinical data base and IWRS data base	Non major
	The gadopiclenol volume actually administered is different from the theoretical one more than 20%	Clinical data base and IWRS	Major
	The gadobutrol volume actually administered is different from the theoretical one more than 20%	Clinical data base and IWRS	Major criteria2
	Temperature excursion for IMP	Monitoring	Non major
	Temperature excursion for gadopiclenol with risk of freezing	Monitoring	Major
	Temperature excursion for gadobutrol with risk of freezing	Monitoring	Major criteria2
	IMP management not appropriate	Monitoring	Non major
	Extravasation during gadopiclenol administration	Clinical data base	Major
	Extravasation during gadobutrol administration	Clinical data base	Major criteria2
	Saline flush not done after IMP administration	Monitoring	Non major
Missing data	Age is missing	Clinical data base	Non major
	Sex is missing	Clinical data base	Non major
	Weight is missing	Clinical data base	Non major
	Height is missing	Clinical data base	Non major
	Ethnicity is missing	Clinical data base	Non major
	Race is missing	Clinical data base	Non major

Category	Description	Source	Status
	eGFR measurement at visit 3 or visit 5 is missing	Clinical data base	Non major
	Central Laboratory Biochemistry results not available	Laboratory data base	Non major
	Central Laboratory Hematology results not available	Laboratory data base	Non major
	Vital sign result missing	Clinical data base	Non major
	Tolerance at injection site is not filled in for patient receiving the study product	Clinical data base	Non major
	No Numeric Pain Intensity Scale completed in case of injection site pain	Clinical data base	Non major

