### 5.7.2. Adverse Events

AEs will be described systematically in terms of number and percentage of patients with AEs and in terms of number of AEs. AEs will be displayed by periods (MRI 1 and MRI 2) and overall.

AEs emergence will be defined as follows:

- Non-treatment emergent AE (NTEAE): if the AE starts prior to the 1st injection (pre-injection) or if the patient is not injected.
- Treatment emergent AE (TEAE): if the AE starts after the 1st injection (post-injection).
  - If it starts between the 1st injection and the 2nd injection (<), then it will be considered as a TEAE associated with the 1st contrast agent of the patient's series (MRI 1).
  - If it starts after the 2nd injection (≥), then it will be considered as a TEAE associated with the 2nd contrast agent of the patient's series (MRI 2).

Time to onset of AE will be calculated as follow: datetime of AE start – datetime of last start time of IMP administration before AE

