### TEAEs

The same table will be displayed by contrast agent groups and periods for Treatment Emergent AEs (TEAEs). The terms “NTEAE” will be replaced by “TEAE”. The following variables will be presented in addition:

- TEAEs with causal relationship to the IMP.
- TEAEs leading to discontinuation of the IMP.
- TEAE leading to IMP unblinding

Same analyses will be repeated by body regions.

The number and percentage of patients with at least one TEAE and the number of TEAE will be presented by contrast agent groups and period and overall according to Primary SOC and PT.

The table will be sorted by descending frequency of SOC and, within each SOC by descending frequency of PT according to the Total column.

Same analyses will be repeated by body regions.

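### SAP 5.7.2 ties adverse events to the agent of the randomised series, while SAP 3.1 calls for the agent actually given; the two rules part for a few foreseeable patients

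*SAP*

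**What the plan says.** SAP 5.7.2 (Adverse Events) is the section that links a treatment-emergent adverse event (TEAE) to a contrast agent. An event between the first and second injection is "considered as a TEAE associated with the 1st contrast agent of the patient's series" and labelled MRI 1. An event from the second injection onwards is "considered as a TEAE associated with the 2nd contrast agent of the patient's series" and labelled MRI 2. Events before any injection, or in patients never injected, are not treatment-emergent.

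Series is the SAP's term for the randomised order. SAP 1.2 says that the randomisation will "allocate patients in a 1:1 ratio to the two series, gadopiclenol-gadobutrol or gadobutrol-gadopiclenol", and SAP 3.1 lists presentation by series separately from presentation by contrast agent group.

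SAP 3.1 then sets a general rule. "For the presentation by contrast agent group", "efficacy analyses will be presented as randomized, that is to say presented by allocated contrast media", and in contrast "safety analyses will be presented by actually administered contrast media". The TEAE tables are laid out by contrast agent group and by period, on the Safety Set, which requires that an injection was received.

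The deviation table in SAP 5.2 provides for departures from allocation. It lists "Patient does not receive the IMP allocated by randomization", and also an MRI carried out without gadopiclenol or without gadobutrol being given. These lead to exclusion from a per-protocol set, not from the Safety Set. Protocol 5.3.1 also gives administration of the wrong product as an example of an allocation problem.

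**The concern.** A programmer deriving the agent for each TEAE will work from 5.7.2. If that section is applied as written, the agent comes from the randomisation list, not from the dosing record. In a patient whose dosing departed from allocation, an event could then be counted under an agent that the patient did not receive.

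The by-agent denominators follow the Safety Set, which SAP 5.2 counts by contrast agent group and which SAP 3.1 makes as-administered. A numerator built by series could therefore contain a patient who is missing from the denominator of the same column. The TEAE and related-TEAE tables by agent are the main safety output, so their derivation should have one reading.

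**Working it through.** No figure in the plan is at issue, so the check is to apply both rules to the same patients. Inputs: the attribution rule in SAP 5.7.2, the as-administered rule in SAP 3.1, the meaning of series in SAP 1.2, and the deviations in SAP 5.2. Take a patient randomised to gadopiclenol first and gadobutrol second.

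| What happened | Event | Agent by 5.7.2, read literally | Agent by 3.1 | Agree? |
|---|---|---|---|---|
| Both injections as allocated | After V2 injection, before V4 injection | gadopiclenol | gadopiclenol | yes |
| Both injections as allocated | After V4 injection | gadobutrol | gadobutrol | yes |
| V2 injection as allocated, no second injection | After V2 injection | gadopiclenol | gadopiclenol | yes |
| Never injected | Any | none (not treatment-emergent) | none | yes |
| Gadobutrol given at V2 in error | After V2 injection, before V4 injection | gadopiclenol | gadobutrol | **no** |
| V2 MRI without injection, gadobutrol at V4 as the only injection | After V4 injection | gadopiclenol | gadobutrol | **no** |

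**Wrong product.** If the patient in the fifth row then receives gadobutrol at V4 as planned, gadopiclenol was never given. By 5.7.2 the event enters the gadopiclenol column, while the as-administered gadopiclenol denominator does not contain the patient. If the two products were simply swapped, both denominators contain the patient and only the attribution is wrong.

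**Missed V2 injection.** The V4 injection is this patient's first. Counting injections received, 5.7.2 gives the first agent of the series and the label MRI 1, although the injection took place at the second MRI. Counting by visit instead gives the second agent and MRI 2, but the SAP does not say to count that way. SAP 3.1 settles the agent column and is silent on the period. Because the tables are split by both, the cell stays wrong or undefined.

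**Size per event.** One misattributed event lowers one agent's count by 1 and raises the other's by 1, so the difference in event counts moves by 1 + 1 = 2. How many such events to expect cannot be derived, because the documents give no number of wrong-product or missed-V2 patients.

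**Wording elsewhere.** Time to onset in 5.7.2 runs from the last product administration before the event. SAP 3.5.4 assigns a same-day procedure to the agent administered that day. Both refer to what was given; the TEAE rule is the one that refers to the series.

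**The case against.** The strongest reply is that the SAP already answers the question. SAP 3.1 sets efficacy as-randomised against safety as-administered, so the choice is deliberate, and the TEAE tables by contrast agent group fall within its scope. On that view 5.7.2 is a timing rule: it defines emergence, its cut-points are the actual injections, and each branch ends in a period label. Section 5.7.2 supplies the period and 3.1 the agent. The agent given is known, because receipt of the wrong product is identified from the clinical and IWRS databases.

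Much of this stands. It is a sensible reading and probably what the authors meant. It does not remove the point, for three reasons. It sets aside the words in 5.7.2 that name an agent. The SAP states no precedence between a general rule and a specific derivation. And 3.1 cannot supply the period label when the V2 injection was missed.

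Two further readings are tempting and fail. A reader might infer that every patient with a single injection is at risk; the third row of the table shows that one given only the first injection, as allocated, is handled correctly. A reader might also see a conflict within 5.7.2 between attribution and time to onset. For an event between the injections the last administration is the first injection, and after the second it is the second, so both rules pick the same injection. They differ only in how the agent is then named.

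**Conclusion.** The contradiction between SAP 5.7.2 and SAP 3.1 is real and minor. It affects patients given the wrong product and patients whose only injection was at V4 after a missed V2 injection. Both are foreseeable under the SAP 5.2 deviations, although SAP 5.2 does not say that a patient with a missed V2 injection would go on to V4. That such patients are few is a judgement; the documents give no count.

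A reader might infer that the SAP has chosen to analyse safety as randomised. The documents do not support that, since 3.1 says the opposite in plain terms. Nor do they support a claim that the safety comparison could be reversed: no number of affected patients is given, and 5.7.2 plans counts, percentages and listings without a between-agent test. The conclusion rests on reading series as SAP 1.2 and 3.1 use it, and on the absence of any stated precedence between the two sections.

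**What to change.** Replace the two sub-bullets under treatment-emergent events in SAP 5.7.2 with:

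*A TEAE is attributed to the contrast agent actually administered at the last injection started at or before AE onset; the period label (MRI 1 / MRI 2) follows the visit of that injection.*

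The words at or before keep the present convention that an event starting at the time of the second injection belongs to that injection. The reference to the patient's series goes. Section 5.7.2 then agrees with 3.1 and with the by-agent Safety Set denominators, and the missed-V2 patient gets a defined period.

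The cost is one sentence and one derivation. Protocol 8.1.2 and 8.1.4 already have injection date and time and the number of the product injected recorded in the eCRF, so no new data are needed.

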### Overall Safety Summary

An overall summary of NTEAEs will be presented using the SPS. The table will be presented with the overall “Total” column only.

The total number of events and number of patients with at least one event was tabulated for the following events :

- All AEs.
- Serious AEs (SAEs) (variable “serious” classified as yes or missing) - patients with AEs having different seriousness criteria will be counted in each category of seriousness criterion.
- AEs of special interest (AESIs) (preferred term is Nephrogenic systemic fibrosis).
- AEs with causal relationship to a trial procedure.
- AEs according to intensity (patients with AEs having different intensities will be counted in each category of intensity).
- AEs according to the outcome (patients with AEs having different outcomes will be counted in each category of outcome).
- AEs requiring a concomitant drug (AE-targeted medication).
- AEs requiring a concomitant procedure/therapeutic measures (other AE-targeted action).
- AEs leading to trial discontinuation.

Furthermore the distribution of the number of AEs reported by patient (0, 1, 2 or 3 or more AEs) will be also presented.

### TEAEs

The same table will be displayed by contrast agent groups and periods for Treatment Emergent AEs (TEAEs). The terms “NTEAE” will be replaced by “TEAE”. The following variables will be presented in addition:

- TEAEs with causal relationship to the IMP.
- TEAEs leading to discontinuation of the IMP.
- TEAE leading to IMP unblinding

Same analyses will be repeated by body regions.

The number and percentage of patients with at least one TEAE and the number of TEAE will be presented by contrast agent groups and period and overall according to Primary SOC and PT.

The table will be sorted by descending frequency of SOC and, within each SOC by descending frequency of PT according to the Total column.

Same analyses will be repeated by body regions.

### **TEAEs with Causal Relationship to the IMP**

The number and percentage of patients with at least one TEAE with causal relationship to the IMP and the number of TEAE will be presented by contrast agent groups and period and overall according to Primary SOC and PT. AEs with causal relationship to the IMP are those described by the investigator with causal relationship to the IMP “related”.

### **TEAEs with Causal Relationship to a Trial Procedure**

The number and percentage of patients with at least one TEAE with causal relationship to a trial procedure and the number of TEAE will be presented by contrast agent groups and period and overall according to Primary SOC and PT. AEs with causal relationship to a trial procedure are those described by the investigator with causal relationship to a trial procedure “related”.

### **Deaths, serious adverse events and other significant adverse events**

Deaths, AESI and SAEs will be listed (if any). These listings will be sorted by patient number, date/time of onset, end date, Primary SOC, High Level Group Term (HGLT), High Level Term (HLT), PT, Lowest Level Term (LLT) and description

Listing of adverse events will be presented in CSR appendix 16.2.7.

### **5.7.3. Clinical laboratory evaluation**

All laboratory values recorded during the trial will be individually listed and flagged for values outside reference ranges if any (presented in CSR appendix 16.2.8). Parameters obtained centrally and those obtained locally will be presented together.

*Hematology data* include the following parameters (in SI and conventional units):

	SI units	Conventional units
Red Blood Cells (RBC) = Erythrocytes	10  /L	10  /µL
White Blood Cells (WBC) = Leukocytes	10  /L	10  /µL
Neutrophils	10  /L	10  /µL
Neutrophils/ Leukocytes	%	%
Eosinophils	10  /L	10  /µL
Eosinophils/ Leukocytes	%	%
Basophils	10  /L	10  /µL
Basophils/ Leukocytes	%	%
Lymphocytes	10  /L	10  /µL
Lymphocytes/ Leukocytes	%	%
Monocytes	10  /L	10  /µL
Monocytes/ Leukocytes	%	%
Platelet count	10  /L	10  /µL
Hemoglobin	g/L	g/dL
Hematocrit	v/v	%
Mean Corpuscular Volume (MCV)	fL	fL

*Biochemistry data* include the following parameters:

	SI units	Conventional units
Sodium	mmol/L	mEq/L
Potassium	mmol/L	mEq/L
Chloride	mmol/L	mEq/L
Blood Urea Nitrogen (BUN)	mmol/L	mg/dL
Urea*	mmol/L	mg/dL
Serum creatinine	umol/L	mg/dL
eGFR	mL/min/1.73m 	mL/min/1.73m 
Total protein	g/L	g/dL
Calcium	mmol/L	mg/dL
Phosphorus	mmol/L	mg/dL
Total bilirubin	umol/L	mg/dL
Indirect bilirubin	umol/L	mg/dL
Conjugated bilirubin	umol/L	mg/dL
Aspartate Amino Transferase (AST)	U/L	U/L
Alanine Amino Transferase (ALT)	U/L	U/L
Alkaline Phosphatase	U/L	U/L
Lactate DeHydrogenase (LDH)	U/L	U/L
Triglycerides	mmol/L	mg/dL
Cystatin C	mg/L	mg/L

\*Urea is derived from BUN. In SI unit, Urea=BUN, in conventional unit, Urea=BUN\*2.14

The baseline value for each laboratory parameter will be the last value measured before the first contrast agent administration (i.e. the assessment prior to 1st MRI).

In the tables and listings, the parameters will be ordered as follow:

- Hematology: Red Blood Cells (RBCs), hemoglobin, hematocrit, Mean red blood Cells Volume (MCV), White Blood Cells (WBCs)=leukocytes, neutrophils, neutrophils/leukocytes, lymphocytes, lymphocytes /leukocytes, monocytes, monocytes/leukocytes, eosinophils, eosinophils/leukocytes, basophils, basophils/leukocytes and platelet count.
- Biochemistry: sodium, potassium, chloride, calcium, phosphorus, total protein, serum creatinine, eGFR, Blood Urea Nitrogen (BUN), Urea, Cystatin C, Aspartate Amino Transferase (AST), Alanine Amino Transferase (ALT), alkaline phosphatase, total bilirubin (and indirect bilirubin), conjugated bilirubin, Triglycerides, Lactate DeHydrogenase (LDH).

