
The number and percentage of patients with at least one AESI with causal relationship to the IMP will be presented using the Safety Set by contrast agent group according to Primary SOC and PT.

11.3.8 ***Laboratory data***

Laboratory data analysis will be done using the Safety Set.

The statistical analysis will present results in standard international units and United States units. Original units will be only listed. Laboratory data will be analyzed quantitatively and qualitatively by contrast agent group. Qualitative analyses will be done via comparison of laboratory data to their reference ranges and according to their clinical significance. Quantitative analyses will be done by tabulating raw data and change from baseline. They will be displayed qualitatively as well by means of shift tables.

11.3.9 ***Other safety observations***

Other safety observations analysis will be done using the Safety Set.

Extent of exposure

Duration between ICF signature, IMP administrations and end of trial will be tabulated by contrast agent group.

Volume actually administered and, actual rate of administration, will be tabulated by contrast agent group.

Injection site tolerance

Number of patients experiencing pain, eruption, extravasation and inflammation at site injection will be tabulated by contrast agent group. Pain at injection site will be measured using the Numeric Pain intensity Scale (NPS) and NPS measurements for these patients will be tabulated by contrast agent group.

Vital signs

Vital signs will be analyzed quantitatively and qualitatively by contrast agent. Qualitative analyses will be done via comparison of vital signs data to their normal ranges (see [section 7.2.11](#)) and according to their clinically significant changes. Quantitative analyses will be done by tabulating raw data and change from baseline.

 CONFIDENTIAL	Protocol No. GDX-44-011 Version No. 3.0 (including amendment 2) June 30, 2020	Page 70 / 82
--	---	--------------

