## ○ Vital signs

Vital signs (supine systolic and diastolic blood pressures, pulse rate) will be measured and recorded according to the following schedules:

- prior to each contrast agent injection (baseline value is measurement prior to the first agent injection)
- At  $60 \pm 15$  minutes following each contrast agent injection
- One day after each contrast injection

- **Injection-site tolerance**

Injection-site tolerance (pain, eruption, extravasation, inflammation, or other) will be assessed over 1 day following each contrast injection (during the injection, 60 min ± 15 min post injection and the day after injection) and over a longer period if the investigator becomes aware of any related AE. In case of injection-site pain, the patient will be asked to specify the level of pain using a Numeric Pain intensity Scale from 0 (no pain) to 10 (maximal pain).

- **Local laboratory parameters**

Serum creatinine and eGFR will be collected according to the following schedules:

- prior to each contrast agent injection (baseline value is from samples collected prior to the first contrast agent injection)
- one day after each contrast agent injection

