#### *Qualitative analysis*

Shift tables presenting relative change from baseline in classes *versus* baseline in classes will be displayed for *serum creatinine*, *eGFR*, *BUN* and *cystatin C*.

Baseline data will be classified as follows (no baseline categories will be used for cystatin C):

SI units	Conventional units

 
• Serum creatinine (umol/L): 
 
○ < 60
 
○ <math>\geq</math> 60 and < 100
 
○ <math>\geq</math> 100
 
 
 
	
 
• Serum creatinine (mg/dL): 
 
• < 0.66
 
• <math>\geq</math> 0.66 and < 1.1
 
• <math>\geq</math> 1.1
 
 
 

 
• eGFR (mL/min/1.73m^2): 
 
○ < 60
 
○ <math>\geq</math> 60 and < 90
 
○ <math>\geq</math> 90
 
 
 
	
 
• eGFR (mL/min/1.73m^2): 
 
• < 60
 
• <math>\geq</math> 60 and < 90
 
• <math>\geq</math> 90
 
 
 

 
• BUN (mmol/L): 
 
○ < 2
 
○ <math>\geq</math> 2 and < 4
 
○ <math>\geq</math> 4 and < 6
 
○ <math>\geq</math> 6
 
 
 
	
 
• BUN (mg/dL): 
 
• < 5.6
 
• <math>\geq</math> 5.6 and < 11.2
 
• <math>\geq</math> 11.2 and < 16.8
 
• <math>\geq</math> 16.8
 
 
 

 
• Cystatin C (U/L): 
 
○ All
 
 
 
	
 
• Cystatin C (U/L): 
 
• All
 
 
 

Relative change from baseline will be calculated as follows:  $100^* \text{ (post injection measurement - baseline measurement) / baseline measurement}$ . Relative change from baseline will be classified as follows:

- $\leq -50\%$ .
- $> -50\%$  and  $\leq -25\%$ .
- $> -25\%$  and  $\leq -15\%$ .
- $> -15\%$  and  $< 0\%$ .
- $\geq 0\%$  and  $< 15\%$ .
- $\geq 15\%$  and  $< 25\%$ .
- $\geq 25\%$  and  $< 50\%$ .
- $\geq 50\%$ .

Numbers and percentages of patients in each class will be presented in both SI and conventional units.

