#### 6.1.3.4 *Laboratory data*

Table 14.3.3.11 Hematology Data - Raw data and Change from Baseline – SI Units – Safety Set

CONFIDENTIAL	STATISTICAL ANALYSIS PLAN PHASE III TRIAL GDX-44-011 VERSION NO. 2.0      DATED 25 JANUARY 2021	████████ Page 53 / 57
--------------	---	--------------------------

Table 14.3.3.2 Hematology Data - Raw data and Change from Baseline – Conventional US Units – Safety Set

Table 14.3.3.3 Biochemistry Data - Raw data and Change from Baseline – SI Units – Safety Set

Table 14.3.3.4 Biochemistry Data - Raw data and Change from Baseline – Conventional US Units – Safety Set

Table 14.3.3.5 Hematology Data - Raw data and Change from Baseline by Body Region – SI Units – Safety Set

Table 14.3.3.6 Hematology Data - Raw data and Change from Baseline by Body Region – Conventional US Units – Safety Set

Table 14.3.3.7 Biochemistry Data - Raw data and Change from Baseline by Body Region – SI Units – Safety Set

Table 14.3.3.8 Biochemistry Data - Raw data and Change from Baseline by Body Region – Conventional US Units – Safety Set

Table 14.3.3.9 Shift Table of Serum Creatinine, eGFR, BUN and Cystatin C between Baseline Measurement and Post-Injection Measurement – SI units – Safety Set

Table 14.3.3.10 Shift Table of Serum Creatinine, eGFR, BUN and Cystatin C between Baseline Measurement and Post-Injection Measurement – Conventional US units – Safety Set

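### Renal shift classes are measured only from the value before the first injection, so if tabulated by agent the second agent's class includes change from before it was given

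*SAP*

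**What the plan says.** SAP 5.7.3 defines the laboratory baseline once for both periods: "The baseline value for each laboratory parameter will be the last value measured before the first contrast agent administration". SAP 2.3 gives the same rule for local creatinine and eGFR ("baseline value is from samples collected prior to the first contrast agent injection") and for the central laboratory parameters. SAP 3.1 and the notes to the Protocol's trial flow chart agree with it. No section defines a second-period baseline.

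The qualitative analysis in SAP 5.7.3 plans "Shift tables presenting relative change from baseline in classes", set against baseline class, for serum creatinine, eGFR, BUN and cystatin C (cystatin C has no baseline categories). The formula is 100 times the bracketed difference over baseline: "post injection measurement - baseline measurement) / baseline measurement". SAP 6.1.3.4 titles the two outputs "Shift Table of Serum Creatinine, eGFR, BUN and Cystatin C between Baseline Measurement and Post-Injection Measurement", one in SI and one in conventional units. Neither the text nor the titles say which visit, period or agent grouping applies.

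The grouping has to be inferred. Protocol 11.3.8 says "Laboratory data will be analyzed quantitatively and qualitatively by contrast agent group" and adds in the same section "They will be displayed qualitatively as well by means of shift tables". SAP 3.1 says that "safety analyses will be presented by actually administered contrast media".

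**The concern.** Each patient receives both agents in random order, so half of the by-agent information comes from the second period. If the shift tables are laid out by agent, the second agent's class is still measured from a sample taken before the first agent was given. Whatever happened to creatinine or eGFR between Visit 2 and Visit 4, including any residual effect of the first injection, is then displayed under the second agent. A reader wanting to know what renal change followed a given agent would see two different quantities in one column: a one-day change after one injection, and a longer change after two.

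The sample that would separate them is already taken. Protocol 8.1.4 collects local creatinine and central laboratory blood at Visit 4 before the injection, but no shift class is planned from it.

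**Working it through.** **Inputs from the documents.** Visit 4 is 2 to 14 days after Visit 2 (Protocol 3.3.1 and 5.3.1). Visits 3 and 5 are each 1 day after an injection. The change formula and class limits (15%, 25% and 50% on the rising side) come from SAP 5.7.3. The plan gives no figure for these tables to reproduce.

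**Span of each change from the Visit 2 baseline, assuming a by-agent layout that uses Visit 3 for the first agent and Visit 5 for the second.**
- First agent, V3 − V2: 1 day, one injection.
- Second agent, V5 − V2 = gap + 1 day: 2 + 1 = 3 days at the shortest and 14 + 1 = 15 days at the longest, two injections.

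**What the second agent's class contains.** V5/V2 = (V4/V2) × (V5/V4). Only the last factor follows the second agent's own injection.
- *Change carried in.* If nothing changes after Visit 4, V5/V4 = 1 and V5/V2 = V4/V2. A V2-to-V4 rise of 15%, 25% or 50% is then shown in the second agent's class starting at 15%, 25% or 50%.
- *Change hidden.* A later rise r is cancelled when V4/V2 = 1/(1 + r), that is, by a prior change of 1/(1 + r) − 1. For r = 15%: 1/1.15 − 1 = −13.0%. For r = 25%: 1/1.25 − 1 = −20.0%. For r = 50%: 1/1.50 − 1 = −33.3%. In each case the table shows 0%.

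**Illustrations (assumed creatinine values, µmol/L).**

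| V2 | V4 | V5 | from V2 | from V4 |
|---|---|---|---|---|
| 80 | 95 | 96 | 16/80 = +20.0% | 1/95 = +1.1% |
| 80 | 64 | 80 | 0/80 = 0.0% | 16/64 = +25.0% |
| 80 | 68 | 80 | 0/80 = 0.0% | 12/68 = +17.6% |

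The first row carries in an earlier rise. In the second and third rows the value rises after Visit 4 but ends where it stood before any exposure. A table from Visit 4 alone would report a shift for a patient with no cumulative change, so neither baseline is enough alone.

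**Sensitivity to assumed variation.** A simulation with no agent effect used an assumed within-patient CV of 5% to 12% and an assumed lasting V2-to-V4 drift with SD 0% to 10%.
- At CV 5% and drift SD 10%, rises of at least 25% at Visit 5 occurred in 3.4% of patients from Visit 2 and 0.1% from Visit 4.
- With no drift the two rates were essentially equal: 0.08% each at CV 5%, and 9.4% versus 9.3% at CV 12%.

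The choice of baseline therefore matters for these rates only to the extent that values really move between Visits 2 and 4. The documents give no figure for that.

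**Does it bias the comparison of agents?** With 1:1 sequences, a common drift d and no residual effect, each agent's mean change contains d in half its patients. The means are A + d/2 and B + d/2, and the difference is A − B. With assumed A = 3 and B = 1 the difference is 2.0 at d = 0, 2 and 5.

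**The case against.** The strongest reply is that this is a deliberate and consistent choice. Both documents use the value before any exposure. In a crossover with a gap as short as 2 days, that value is the only one that cannot absorb a residual effect of the first agent, and it shows cumulative change. That stands: the third illustration above is a case where a Visit 4 baseline alone would mislead.

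Existing outputs also give partial cover. SAP 5.4.4 tabulates eGFR at Visits 2 and 4 by agent, in classes. Protocol 8.1.3 to 8.1.5 require creatinine to be assessed at Visits 3, 4 and 5, and SAP 5.7.2 attributes an adverse event to an agent by its onset. SAP 5.7.3 summarises laboratory values at Visits 2 to 5, counts clinically significant values by agent and lists every value. All of this stands. Shift classes cannot be rebuilt from the summary tables, but V4-to-V5 changes can be computed from the listings.

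Three stronger readings are tempting, and the documents do not support them.
- *The plan misattributes renal shifts as a matter of fact.* The by-agent layout is an inference from Protocol 11.3.8 and SAP 3.1. The shift-table text omits it, although the next paragraph of SAP 5.7.3 states it for clinically significant values. A layout by visit or period would let a reader see which rows follow two injections.
- *One agent is favoured.* Common mean drift cancels under 1:1 sequences, and no directional bias has been shown.
- *The tables fail the Protocol's definition of post-contrast kidney injury.* Protocol 7.2.11 cites a 48 to 72 hour window but leaves clinical significance to the investigator, and the SAP does not tie the shift tables to that definition.

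The simulation also found that 39% to 72% of patients changed class between the two baselines. That range deserves little weight: it rests on assumed variation, and because one class limit is 0%, trivial noise around zero counts as a change of class.

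**Conclusion.** The point holds as a minor improvement to descriptive safety output. The single baseline is certain from the text. That the second agent's class mixes two injections over 3 to 15 days depends on the by-agent layout, which is implied but not stated, and on Visit 5 being the measurement used. Under that layout, a class can display a change that arose before the second injection or hide one that arose after it. The size of any such effect in this trial cannot be derived from the documents, and no frequency is claimed.

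The baseline is not wrong and the documents do not contradict each other. Efficacy, adverse-event attribution and the listings are unaffected. The missing statement of visit, period and grouping needs settling in any case. As written, even a Visit 4 sample, taken after the first injection and before the second, could count as a post-injection measurement.

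**What to change.** In SAP 5.7.3:

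1. Add renal shift tables by agent, in SI and conventional units, with change measured from the last value before that agent's own injection: Visit 3 against Visit 2 pre-injection for the first agent, and Visit 5 against Visit 4 pre-injection for the second. Take the baseline class from the same value for the parameters that have classes.
2. Keep the two Visit 2-based tables, 14.3.3.9 and 14.3.3.10 in SAP 6.1.3.4, as the display of cumulative change.
3. State in the text and in every shift-table title the visit, period and agent grouping used.

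The cost is a few lines of SAP wording and two extra descriptive tables. The samples are already collected, and trial conduct and sample size do not change. The drawback is that a Visit 4 baseline can absorb a residual effect of the first agent, which is why both versions should be shown. Haematology and vital signs need no change for this point.
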